Purpose	The primary purposes of the study are (1) to provide salvage therapy for individuals who previously participated in a peanut immunotherapy trial but did not demonstrate clinically significant desensitization, (2) to investigate the safety and tolerability of the salvage therapy regimen including both peanut flour and peanut flour equivalent, and (3) to explore mechanisms responsible for long-term desensitization and/or tolerance to food allergens induced by immunotherapy.
Study Design	This uncontrolled, observational, prospective, open-label study will be used to assess the safety and tolerability of a two-stage salvage therapy regimen: (a) peanut oral immunotherapy (OIT) followed by (b) extended maintenance with a peanut food equivalent.
Participants	We will enroll up to 100 eligible subjects who (1) did not demonstrate clinically significant desensitization in previous peanut immunotherapy trials, or (2) previously endured an extended time on placebo therapy, or (3) previously developed desensitization and then subsequently lost this protection due to time off from therapy.
Choice of Sample Size	The choice of sample size is based entirely on the ethical necessity of providing therapy to a pre-defined number of

	individuals in need of salvage therapy. We anticipate that up to 100 eligible subjects will be enrolled to receive the salvage therapy treatment regimen.
Study Duration	Approximately 12 months for each participant.
Primary Outcomes	
 Overall incidence rate of adverse events (including both AEs and SAEs) during the entire 2-stage treatment sequence Overall number of days of treatment missed during the entire 2-stage treatment sequence
Secondary Outcomes	
 Stage-specific incidence rate of all adverse events Days of treatment missed during each stage of treatment. Overall incidence rate of gastrointestinal AEs during the entire 2-stage treatment sequence. Overall incidence rate of Epipen use Overall incidence rate of drop-outs due to gastrointestinal AEs during the entire 2-stage treatment sequence.
Exploratory Measures	
 Changes in basophil, T cell, and antibody responses in peripheral blood and saliva samples (to explore the mechanisms responsible for long-term desensitization and/or tolerance to food allergens induced by immunotherapy.)
Inclusion Criteria	
 Subjects who have completed an immunotherapy trial for peanut allergy within the last 18 months and are unable to tolerate $\geq 300\text{mg}$ of peanut. Age 1-65 years of either sex, any race, any ethnicity. Written informed consent from patient or parent/guardian (if < 18 years) with participant's assent.
Exclusion Criteria	
 Current participation in an interventional study for peanut allergy History of a severe anaphylactic reaction to peanut, defined as hypoxia, hypotension, or neurologic compromise (cyanosis or $\text{SpO}_2 < 92\%$ at any stage, hypotension, confusion, collapse, loss of consciousness, or incontinence)

	
 • Eosinophilic or other inflammatory (e.g. celiac) gastrointestinal disease • Severe asthma (2007 NHLBI Criteria Steps 5 or 6 – Appendix 2) • Use of β-blockers (oral), angiotensin-converting enzyme (ACE) inhibitors, angiotensin-receptor blockers (ARB) or calcium channel blockers • Significant medical condition (e.g., liver, kidney, gastrointestinal, cardiovascular, hematologic, or pulmonary disease) which would put the subject at risk for induction of severe food reactions. • Pregnancy or lactation.
Study Procedures	
The following procedures will be performed:
 
 • Medical and allergy history (including dietary history) • Physical examination • Peak flow rates (if capable) • Oral immunotherapy (OIT) • Serum analysis for peanut-specific immunoglobulins (ImmunoCAP) (optional) • Peanut skin prick testing (optional) • Saliva collection (optional) • Pregnancy test for females in childbearing age.

GLOSSARY OF ABBREVIATIONS

AE	Adverse Event
CTCAE	Common Toxicity Criteria Adverse Event
CFR	Code of Federal Regulations
CRF	Case Report Form
CTR	Clinical Translational Research Center
DBPCFC	Double Blind Placebo Controlled Food Challenge
DSMB	Data Safety Monitoring Board
FASC	Food Allergy Study Center
FDA	Food and Drug Administration
GCP	Good Clinical Practice
GMP	Good Manufacturing Practice
HRQL	Health-Related Quality of Life
ICH	International Conference on Harmonization
IND	Investigational New Drug
IRB	Institutional Review Board
NIAID	National Institute of Allergy and Infectious Diseases
OFC	Oral Food Challenge
OIT	Oral Immunotherapy
PI	Principal Investigator
SAE	Serious Adverse Event
SPT	Skin Prick Test
SU	Sustained Unresponsiveness
UNC	The University of North Carolina at Chapel Hill

1. BACKGROUND AND RATIONALE

A. BACKGROUND

Food allergy is a significant public health problem that is increasing in prevalence. According to recent CDC data, approximately 4% of children are affected by food allergy while 1.3% of the total population is allergic to peanut or tree nuts. Despite recent increased recognition and understanding of the disease, food allergy is the most common cause of outpatient anaphylaxis, and peanut allergy is the most common cause of fatal anaphylaxis. In the United States, it is estimated that emergency departments treat about 30,000 food-induced anaphylactic events each year, and that about 200 fatal cases occur annually.

Currently the only available preventative treatment for food allergy is strict avoidance of the allergenic food. Food avoidance involves a lifestyle change for families, requiring careful reading of food labels, exercising caution when dining at restaurants, and carrying rescue medications at all times. For these reasons, food allergy is known to significantly impact the quality of life for both patients and their families. These findings stress the importance of developing improved therapies for food allergy.

B. RATIONALE

An increasing number of studies have proved the concept that peanut immunotherapy can desensitize subjects with peanut allergy by regulating their mucosal and systemic immune reactivity. This has culminated in the development of a large phase 3 study of peanut OIT that is currently underway with guidance from the US Food and Drug Administration (FDA). However, there are important aspects of peanut OIT that remain to be studied and are the subject of more recent studies. These include questions about the durability of the desensitization effect termed sustained unresponsiveness (SU), the effect of peanut OIT in special populations such as very young children, and the prevalence of certain side effects such as eosinophilic esophagitis. With this gradual shift away from equipoise, a need

for providing a salvage therapy option for those who continue to volunteer to participate in research studies has become apparent. Two populations of particular interest are those who have previously developed desensitization and then subsequently lost this protection and those who have been randomized to extended courses of placebo drug.

In many current studies of peanut OIT, subjects are initially desensitized and then subsequently asked to avoid peanut for a discrete amount of time in order to assess the durability of the desensitization effect (sustained unresponsiveness). This research is critical to understanding the clinical and immunologic changes induced by peanut OIT and longer term implications of therapy. However, in the course of these investigations, the potential exists for subjects to lose their desensitization to peanut and their protection against accidental exposures to peanut.

The majority of current studies of OIT utilize a placebo group, some for extended periods of time (> 1 year). These extended placebo courses are vital to understanding the efficacy of OIT as up to 20% of peanut-allergic patients are thought to naturally develop tolerance to peanut. These subjects are not thought to be at any higher risk than those who are strictly avoiding peanut which is the current standard of care. However, concerns remain with withholding potentially protective treatment for these extended periods of time.

The use of investigational drugs to induce and maintain desensitization has been and continues to be the subject of numerous ongoing studies. However, there has been growing interest in the use of food products to maintain this effect with the thought that these readily available foods may allow for superior compliance. The safety and compliance with transitioning to a non-drug equivalent amount of peanut food has not been well studied.

The goals of this study protocol are several-fold. First and foremost, we would like to provide a salvage therapy option for those previously involved in vital peanut allergy research. Simultaneously, we will address three research aims:

Aim 1 --Investigate the safety and compliance in the 2-stage protocol in subjects who either (a) have previously developed desensitization and then subsequently lost this protection due to a period of time off of therapy or (b) have previously endured an extended time on placebo therapy.

Aim 2 -- Characterize and compare the two stages of the protocol in terms of safety and compliance.

Aim 3 -- Explore the mechanisms responsible for long-term desensitization and/or tolerance to food allergens induced by immunotherapy.

In doing this, we aim to add to the accumulating pool of data on the safety of OIT while providing a salvage option for these subjects. The data generated from our study can guide future research to identify high risk groups for peanut oral immunotherapy, and compare safety and compliance between peanut OIT and peanut food equivalents. A food equivalent of peanut containing food is an available food in the market with known doses of peanut protein (e.g. Reese's peanut butter cups, Peanut M&Ms, etc.)

2. POTENTIAL RISKS AND BENEFITS

A. RISKS

The main risks for participating in this study include:

1. Allergic symptoms during the initial escalation, build up or maintenance phase: including sneezing, rhinorrhea, urticaria, angioedema, flushing, eczema flare, nausea, vomiting, diarrhea, abdominal discomfort, cough, wheezing, dyspnea, pruritus (ocular, nasal, oral, throat) or anaphylaxis.
2. Skin prick testing (SPT) is an optional procedure in the study and may result in a small, pruritic hive where the test is placed. Usually, the hives resolve within 1-2 hours, but rarely a subject may have local swelling that takes two to three days to clear entirely. Very rarely, some individuals may develop a serious allergic reaction that is life threatening, but no deaths from prick skin testing using standard dosing techniques have been reported in fifty years. Skin prick testing will be supervised by a physician or nurse coordinator, and rescue medications will be readily available if any reaction occurs.
3. Blood draws for mechanistic studies are an optional procedure in the study and result in pain and discomfort, bleeding, bruising where the needle is placed, and, in rare cases, fainting and infection. In order to minimize the risk of anemia, the maximum volume of blood to be drawn will be less than 2 ml/kg of body weight per visit up to a maximum of 45 ml in 8-week period for pediatrics and less than 550 ml in an 8-week

period for adults. This maximum amount applies for both clinical or research purposes: clinical blood draw will be considered prior to research blood draw). Blood collection will not occur more than 2 times per week.

B. BENEFITS

The benefits from this study include:

1. The potential of decreasing the participants' reactivity to peanut after an accidental ingestion by developing desensitization to at least an equivalent of the daily tolerated maintenance dose (300 mg of peanut protein). Most accidental exposures to peanut protein are believed to be less than 200 mg. (Schäppi, GF et al. 2001).
2. This study will expand the general knowledge of food allergy. This applies specifically to safety of peanut oral immunotherapy and identifying high risk groups. This may lead to new management and therapeutic protocols for individuals with peanut allergy, or food allergy in general.

3. OBJECTIVES AND OUTCOME MEASURES

A. OBJECTIVES

1. The primary objective of this study is to place patients who have been involved in peanut immunotherapy research on salvage therapy while investigating safety and compliance of oral immunotherapy and food equivalent therapy in these patients.
2. The secondary objectives include:
 - a. Investigation of incidence of gastrointestinal adverse event, drop outs, and Epipen use.
 - b. Investigation of the compliance of participation with peanut OIT and peanut food equivalent

B. OUTCOME MEASURES

1. Primary Outcomes
 - Overall incidence rate of adverse events (including both AEs and SAEs)

during the entire 2-stage treatment sequence (OIT followed by peanut containing food equivalent)

- Overall number of days of treatment missed during the entire 2-stage treatment sequence

2. Secondary Outcomes

- Stage-specific incidence rate of all adverse events
- Days of treatment missed during each stage of treatment.
- Overall incidence rate of gastrointestinal AEs during the entire 2-stage treatment sequence.
- Overall incidence rate of Epipen use
- Overall incidence rate of drop-outs due to gastrointestinal AEs during the entire 2-stage treatment sequence.

4. SELECTION AND WITHDRAWAL OF PARTICIPANTS

A. INCLUSION CRITERIA

Anyone meeting all of these criteria is eligible for enrollment as study participants:

1. Age 1-65 years of either sex, any race, any ethnicity.
2. Subjects who have completed an immunotherapy trial for peanut allergy within the last 18 months and are unable to tolerate $\geq 300\text{mg}$ of peanut.
3. Written informed consent from patient (if ≥ 18 years) or permission of parent/guardian with participant's assent (if between 7-17)

B. EXCLUSION CRITERIA

Participants who meet any of these criteria are not eligible for enrollment as study participants:

1. History of a severe anaphylactic reaction to peanut, defined as hypoxia, hypotension, or neurologic compromise (cyanosis or $\text{SpO}_2 < 92\%$ at

any stage, hypotension, confusion, collapse, loss of consciousness, or incontinence)

2. Eosinophilic or other inflammatory (e.g. celiac) gastrointestinal disease
3. Severe asthma (2007 NHLBI Criteria Steps 5 or 6 – Appendix 2)
4. Use of β -blockers (oral), angiotensin-converting enzyme (ACE) inhibitors, angiotensin-receptor blockers (ARB) or calcium channel blockers
5. Significant medical condition (e.g., liver, kidney, gastrointestinal, cardiovascular, hematologic, or pulmonary disease) which would put the subject at risk for induction of severe food reactions.
6. Currently participation in an interventional study for peanut allergy.
7. Pregnancy or lactation.

C. PREMATURE WITHDRAWAL CRITERIA

Participants may be prematurely withdrawn from the study if:

1. At any point in the study, the participant elects to withdraw consent from all future study activities.
2. The participant is “lost to follow-up” (i.e., no further follow-up is possible because attempts to reestablish contact with the participant have failed).
3. The participant develops a medical condition that the investigator deems incompatible with participation in the trial. That includes specifically developing Eosinophilic Esophagitis (participants who develop symptoms compatible with Eosinophilic Esophagitis will be referred to a gastroenterologist).
4. Severe atopic dermatitis requiring oral steroids or immunmodulatory agent, or severe asthma; requiring more than daily medium dose inhaled corticosteroids (more than Flovent 440 mcg daily or its equivalent)
5. The use of systemic corticosteroids in the past 30 days.
6. The participant experiences severe symptoms during the build-up or maintenance phases as a result peanut OIT dosing

7. In the investigator's discretion, there is poor compliance or any other concern that would create an unacceptable risk to the subject.

8. The participant dies.

9. The study ends.

To the extent possible, participants who discontinue therapy will be followed to observe and record study outcomes.

D. STUDY TERMINATION CRITERIA

If any of the stopping rules listed below are met, study enrollment will be suspended, the initial dose escalation phase and build-up phase will be stopped, and all enrolled participants will remain on their current dose pending expedited review of all pertinent data by the Data Safety Monitoring Board:

1. Any death related to peanut OIT dosing.
2. More than one event comprising systemic allergic symptoms with significant hypotension at any stage of the protocol.
3. More than 3 participants require more than 2 injections of epinephrine during dosing of the peanut product.
4. More than 3 of the following events:
 - Severe adverse event, other than anaphylaxis, related to investigational product.
 - Eosinophilic esophagitis.

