2. ESCALATION PHASE

All subjects will undergo a one-day peanut desensitization protocol to enable them to tolerate a daily dose of peanut protein (3-6 mg) (Table I). If the participant has a reaction to one of the doses in the escalation, the next dose will be determined at the discretion of the investigator. The options open to the investigator are to administer the last previously tolerated dose, or wait an additional amount of time between doses. Once this determination of the dosage amount is made, the desensitization process resumes as outlined.

Upon completion of the modified escalation phase to peanut, the subject is observed for a minimum of 2 hours. If there is no evidence of an allergic reaction the subject is discharged home. If the subject requires treatment for symptoms during the initial escalation protocol with antihistamines on one occasion, then the rest of the protocol may be followed. If the subject requires more than one medication or multiple doses of antihistamines or requires other rescue medications, the initial desensitization phase should be stopped. If the subject has tolerated either the 3 mg or 6mg dose, the subject will be eligible to return on Day 2 to proceed with the build-up phase. Subjects must be able to tolerate the first two doses of escalation with mild or no symptoms to continue with build-up.

Table I

Dose #	Dose	Interval (minutes)	% Increase
1	1.5mg	30	100
2	1.5mg	30	0
3	3mg	30	100
4	6mg	30	100

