Anaphylaxis:

Anaphylaxis will be defined according to second National Institute of Allergy and Infectious Disease/ Food Allergy and Anaphylaxis Network symposium (Sampson H, Muñoz-Furlong A, Campbell R, *et al.* 2006. Second symposium on the definition and management of anaphylaxis: Summary report: Second National Institute of Allergy and Infectious Diseases/Food Allergy and Anaphylaxis Network symposium. *J Allergy Clin Immunol*. 92:397–403) as following:

Table I. Clinical criteria for diagnosing anaphylaxis

Anaphylaxis is highly likely when any one of the following 3 criteria are fulfilled:

1. Acute onset of an illness (minutes to several hours) with involvement of the skin, mucosal tissue, or both (eg, generalized hives, pruritus or flushing, swollen lips-tongue-uvula)

AND AT LEAST ONE OF THE FOLLOWING

a. Respiratory compromise (eg, dyspnea, wheeze-bronchospasm, stridor, reduced PEF, hypoxemia)

b. Reduced BP or associated symptoms of end-organ dysfunction (eg, hypotonia [collapse], syncope, incontinence)

2. Two or more of the following that occur rapidly after exposure **TO A LIKELY ALLERGEN FOR THAT PATIENT** (minutes to several hours):

a. Involvement of the skin-mucosal tissue (eg, generalized hives, itch-flush, swollen lips-tongue-uvula)

b. Respiratory compromise (eg, dyspnea, wheeze-bronchospasm, stridor, reduced PEF, hypoxemia)

c. Reduced BP or associated symptoms (eg, hypotonia [collapse], syncope, incontinence)

Anaphylaxis is highly likely when any one of the following 3 criteria are fulfilled:

- d. Persistent gastrointestinal symptoms (eg, crampy abdominal pain, vomiting)
- 3. Reduced BP after exposure to **KNOWN ALLERGEN FOR THAT PATIENT** (minutes to several hours):
 - a. Infants and children: low systolic BP (age specific) or greater than 30% decrease in systolic BP*
 - b. Adults: systolic BP of less than 90 mm Hg or greater than 30% decrease from that person's baseline

PEF, Peak expiratory flow; **BP**, blood pressure.

* Low systolic blood pressure for children is defined as less than 70 mm Hg from 1 month to 1 year, less than (70 mm Hg + [2 × age]) from 1 to 10 years, and less than 90 mm Hg from 11 to 17 years.

Eosinophilic Esophagitis:

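### No stopping rule in section 4.D counts a single non-fatal anaphylaxis with hypoxia but without significant hypotension, treated with one or two epinephrine injections, however many participants have one

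*Combined protocol and SAP*

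**What the plan says.** Section 4.D lists four study-level triggers. If any is met, enrollment is suspended, initial escalation and build-up stop, and "all enrolled participants will remain on their current dose pending expedited review of all pertinent data" by the DSMB. The triggers are:

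- Rule 1: a death related to peanut OIT dosing.
- Rule 2: "More than one event comprising systemic allergic symptoms with significant hypotension at any stage of the protocol".
- Rule 3: "More than 3 participants require more than 2 injections of epinephrine during dosing of the peanut product".
- Rule 4: more than three events that are either eosinophilic esophagitis or a "Severe adverse event, other than anaphylaxis, related to investigational product".

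Exclusion criterion 4.B.1 bars people with a "History of a severe anaphylactic reaction to peanut, defined as hypoxia, hypotension, or neurologic compromise", and gives cyanosis or SpO2 below 92% as the marker of hypoxia. The anaphylaxis criteria in section 8.B list hypoxemia in the respiratory limb, "Respiratory compromise (eg, dyspnea, wheeze-bronchospasm, stridor, reduced PEF, hypoxemia", separately from the limb for reduced blood pressure.

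Outside 4.D, several provisions respond to a severe reaction. In the escalation phase (5.D.2), if the participant "requires other rescue medications, the initial desensitization phase should be stopped". Severe symptoms in build-up end participation (5.D.3). Section 4.C item 6 allows withdrawal if "The participant experiences severe symptoms during the build-up or maintenance phases as a result peanut OIT dosing", and item 7 allows it at the investigator's discretion. Sections 8.E and 8.F provide for 24-hour notice of SAEs to the DSMB, expedited reports to the FDA, IRB and DSMB, and power for the DSMB or IRB to suspend.

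**The concern.** Anaphylaxis is named among the main risks in section 2.A, participants take the allergen every day, and adverse events are a primary outcome. Stopping rules exist so that a cluster of grave reactions leads to a pause and review without anyone having to decide that it should. Here two reactions with significant hypotension force that review. Two, ten or more reactions with hypoxia at preserved blood pressure, one per participant and each treated with one or two injections, do not. The protocol regards a past reaction of that kind as grave enough to bar entry, and gives no reason for keeping hypotension and leaving out hypoxia once dosing starts. The exclusion should lower the rate of hypoxic reactions on study, but it does not remove the risk.

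**Working it through.** **Step 1: run the event through the rules.** Take k participants, each with one non-fatal anaphylaxis with hypoxia, no significant hypotension and e injections, where e is 1 or 2.

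| Rule in 4.D | Threshold | Count from k such participants | Met? |
|---|---|---|---|
| 1 | at least 1 related death | 0 | no |
| 2 | at least 2 events with significant hypotension | 0 | no |
| 3 | at least 4 participants with at least 3 injections | 0 | no |
| 4 | at least 4 events, anaphylaxis excluded | 0 | no |

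The result is the same for every k from 1 to 100, the enrollment ceiling in section 10.C. As a check on the logic, with e = 3 rule 3 is met once k reaches 4. This step needs no assumed rate.

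**Step 2: test other readings.** Hypoxia cannot be read into rule 2, because 8.B keeps hypoxemia apart from reduced blood pressure; skin involvement plus hypoxemia is anaphylaxis at a normal blood pressure. Rule 3 does not say whether injections are counted per reaction or cumulatively. Read cumulatively, a participant with repeat reactions could count, but one with a single reaction and one or two injections still does not.

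**Step 3: illustrate the size.** The plan gives no event rates and no operating characteristics for the rules, so there is no figure to reproduce. Assume independent participants with at most one such event each. Let r be the rate of events that a rule 2 widened to hypoxia would count, and f the share of those that only the widened rule counts. With p the per-participant probability of a counted event,

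P(rule 2 met) = 1 − (1 − p)^n − n·p·(1 − p)^(n−1),

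where p = r for the widened rule and p = r(1 − f) for the rule as written.

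For n = 100 and r = 1%:

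- Widened, p = 0.01: 1 − 0.3660 − 0.3697 = 0.264.
- As written, f = 10%, p = 0.009: 1 − 0.4049 − 0.3677 = 0.227.
- As written, f = 25%, p = 0.0075: 1 − 0.4710 − 0.3559 = 0.173.
- As written, f = 50%, p = 0.005: 1 − 0.6058 − 0.3044 = 0.090.

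The same formula at other rates, n = 100:

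| r | Widened | As written, f = 10% | f = 25% | f = 50% |
|---|---|---|---|---|
| 0.5% | 0.090 | 0.075 | 0.055 | 0.026 |
| 1% | 0.264 | 0.227 | 0.173 | 0.090 |
| 2% | 0.597 | 0.539 | 0.443 | 0.264 |

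**Step 4: chance of a cluster that passes uncounted.** Let U be the number of events only the widened rule counts (probability rf per participant) and H the number already counted (probability r(1 − f)). The cluster of interest is U ≥ 2 with H ≤ 1:

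P = Σ over h = 0, 1 of P(H = h) · P(U ≥ 2 | H = h), with U given H = h binomial on n − h participants with probability rf / (1 − r(1 − f)).

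For n = 100 and f = 10%, 25%, 50%, this gives 0.004, 0.022, 0.082 at r = 1%, and 0.008, 0.051, 0.196 at r = 2%.

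**The case against.** The strongest reply is that this is a deliberate clinical choice. Rule 4 leaves out anaphylaxis because it is an expected reaction to daily allergen, and rules 1 to 3 bring back what the sponsor saw as its worst forms. Nothing in the protocol says that stopping rules must mirror an entry criterion, and 4.B.1 is the only place that treats hypoxia on its own as severe: the Grade 4 description in 8.B ties it to decreased consciousness with collapse or incontinence. This stands in part. The rule 4 exclusion does look intended and should stay. A reader might infer that 4.D contradicts 4.B.1; it does not, since a screen and a stopping rule can differ. What remains is that rule 2 takes up only part of the protocol's own description of severe anaphylaxis, without explanation.

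The second reply is that the event is handled elsewhere. Hypoxic anaphylaxis would plausibly meet the broad SAE definition in 8.A. The DSMB would then hear of it within 24 hours and could suspend the study, and the participant may be stopped individually. This also stands, and it rules out the tempting inference that such reactions would escape the DSMB. Reliance on periodic listings and an annual meeting arises only for an event not judged serious. But the individual measures act on one participant, and suspension by the DSMB or IRB is discretionary. None is a preset study-level trigger.

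The third reply is that r and f are invented. That is correct; at f = 10% an uncounted cluster is improbable, and the figures only show how the rule behaves. A reader might also infer that every neurologic sign in 4.B.1 goes uncounted. The documents do not support that: 8.B places collapse, syncope and incontinence in the reduced-blood-pressure limb, so rule 2 may already count them.

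**Conclusion.** The gap follows from the text of 4.D alone. For this event type the number of affected participants is irrelevant to all four triggers. It is a narrow gap: what is missing is the automatic pause with expedited review, not individual protection and not DSMB awareness of an event judged an SAE. Its practical size cannot be fixed from the documents. Under the stated assumptions, with 100 participants and r = 1%, widening rule 2 adds 0.037 (f = 10%), 0.091 (f = 25%) or 0.174 (f = 50%) to the chance that it is met. These figures assume independent participants, one event each, full enrollment, and that every event is recognized. They also take all the events that only the widened rule counts as not counting toward rule 3. The change is worth making because it is cheap and uses a term that the protocol already defines, not because the trial lacks safety oversight.

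**What to change.** In rule 2 of section 4.D, directly after the reference to significant hypotension, insert *or hypoxia (cyanosis or confirmed SpO2 <92%)*, leaving the rest of the rule and its threshold unchanged. The word *confirmed* keeps a stray oximeter reading from counting. Keep the rule 4 exclusion of anaphylaxis. In section 5.D.3, state that SpO2 is among the vital signs already taken whenever symptoms occur in clinic; the present text does not say so. Leave to the sponsor and DSMB whether neurologic compromise should be added, and whether collapse or incontinence already counts under rule 2. If the limit to hypotension was intended, a sentence giving the reason would be enough.

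The cost is one amended rule, one clarified procedure, and a somewhat higher chance of a temporary pause, by the amounts given above. During a pause, enrollment, escalation and build-up stop while enrolled participants stay on their current dose. Home reactions depend on families recognizing cyanosis and recording it in the diary (section 5.G), so some would still be missed.
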